COMPARISON OF BENZALKONIUM CHLORIDE CONTAINING ALBUTEROL VERSUS PRESERVATIVE FREE ALBUTEROL FOR THE TREATMENT OF STATUS ASTHMATICUS

BACKGROUND

In 2014, the Centers for Disease Control and Prevention reported approximately 6.3 million children in the United States with a diagnosis of asthma.¹ According to the National Heart, Lung, and Blood Institute, inpatient management of an acute asthma exacerbation may include continuous albuterol administration.² Due to higher dosing requirements over an extended duration of time, continuous albuterol administration requires a larger volume of albuterol solution, which is often obtained from a multi-dose vial containing benzalkonium chloride (BAC). BAC is a common preservative used in pharmaceuticals, but also considered to be a potent bronchoconstrictor. BAC doses as low as 124 micrograms have been shown to cause bronchoconstriction. This effect is cumulative, prolonged, and correlates directly with basal airway responsiveness.³ The multi-dose albuterol vials currently used for continuous albuterol administration contain 50 micrograms of BAC per 2.5 milligrams of albuterol. A patient receiving continuous albuterol inhalation at 20 milligrams per hour will receive 400 micrograms of BAC per hour. In the 1999 study conducted by Asmus et al., the mean concentration of BAC required to provoke a 20% drop in FEV₁ was 300 micrograms (range 124 to 1947 micrograms).⁴ This raises concern that the bronchoconstricting effects of BAC may antagonize the therapeutic goals of albuterol therapy among patients receiving continuous albuterol inhalation for extended periods of time.

OBJECTIVE

The primary objective of this study is to compare the length of continuous albuterol administration between patients receiving BAC-containing albuterol (BAC-albuterol) versus preservative free albuterol (PF-albuterol). Secondary objectives include comparison of therapy escalation, asthma scores, forced expiratory volume in one second (FEV₁) at discharge, length of hospital stay, and cost.

METHODS

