Data gathered pertaining to continuous albuterol administration will include albuterol formulation, dose, length of therapy, cost of medication administered, and amount of BAC administered.

Additional parameters obtained will include admission asthma score, escalation of therapy related to asthma exacerbation, time on supplemental oxygen, transfer to higher acuity care, total hospital length of stay, and discharge FEV₁.

A data collection document will be used by the respiratory therapist to collect start/stop time of continuous albuterol, evidence of patient non-adherence, and re-initiation of continuous albuterol. After completion, this document will be stored in a binder, in a cabinet, within a locked office. All data (from the data collection form and from the electronic medical record) collected will be stored in an Excel spreadsheet for data analysis. The data collection sheet to be used is attached. Data collected will be stored on a password protected computer, within a locked office, and will be restricted to the primary investigator. All information will be de-identified once entered into the data collection sheet.

STATISICAL ANALYSIS

A power analysis will be conducted in order to determine the sample size needed to detect a statistical difference between groups. Descriptive statistics will be used to evaluate population demographics, while comparison data will be analyzed using a two-tailed student t-test.

CITATIONS

1. National Center for Health Statistics. Asthma, United States, 2014: Morbidity: Children (under age 18 years). Hyattsville, Maryland. 2014
2. Guidelines for the Diagnosis and Management of Asthma (EPR-3). NHLBI, NIH. National Institutes of Health, July 2007

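### The primary duration has no rule for courses that end in escalation, transfer or non-adherence, or that restart, so failures can count as short courses and mask harm from BAC

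*Combined protocol and SAP*

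**What the plan says.** The objective section of the combined protocol and SAP states: "The primary objective of this study is to compare the length of continuous albuterol administration between patients receiving BAC-containing albuterol", with preservative-free albuterol as the comparator. The plan does not say in words that a shorter course is better. That follows from the background, which is concerned that "the bronchoconstricting effects of BAC may antagonize the therapeutic goals of albuterol therapy".

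The data collection section describes the respiratory therapist's form: "A data collection document will be used by the respiratory therapist to collect start/stop time of continuous albuterol, evidence of patient non-adherence, and re-initiation". The form is said to be attached, but it is not part of the text available for this review.

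The same section lists further parameters, among them "escalation of therapy related to asthma exacerbation, time on supplemental oxygen, transfer to higher acuity care". Escalation is also a secondary outcome: "Secondary objectives include comparison of therapy escalation, asthma scores". The electronic record is a second source: "All data (from the data collection form and from the electronic medical record) collected will be stored in an Excel spreadsheet".

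The statistical analysis section gives a two-tailed t-test for comparisons and defers the sample size to a later power analysis. No section says:

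- whether timing ends when a child is transferred;
- how a stop that is not a recovery is counted;
- how a restarted course is counted.

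**The concern.** Time on treatment measures recovery only if treatment stops because the child has recovered. Suppose one child is weaned at 6 h, and another has a recorded course that ends at 6 h because of transfer or replacement by other therapy. Both enter the t-test as 6 h, although one did well and the other did not. A child who stops through non-adherence also looks like a quick recovery.

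This error need not be equal between arms. If BAC works against albuterol, as the background fears, failures should be more frequent on BAC. Each failure that shortens the recorded course lowers the BAC mean, so the bias runs against the effect the study is looking for and grows with the excess of failures.

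Restarts add a second ambiguity. The duration could be the first course only, the sum of courses, or the span from first start to last stop, and a child who relapses scores differently under each.

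**Working it through.** The plan states no duration, SD, failure rate, effect size or sample size, so there is no figure to reproduce. Every input below is an assumption, and the results show size and direction only.

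**Effect on the mean difference.** Assumed inputs:

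- True durations are lognormal with mean m = 20 h (BAC) and 17 h (preservative-free, PF), and SD 60% of the mean.
- A share f of each arm fails, and a failed course is recorded as ending at c = 6, 12 or 18 h if it would have run longer.
- Failures come either from the longest third of courses or from all courses at random.

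Let L be the mean number of hours cut from a failed course. The recorded mean is m − f·L, so:

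recorded difference (BAC − PF) = 3.0 − f_BAC·L_BAC + f_PF·L_PF

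The lognormal parameters are σ² = ln(1 + 0.6²) = 0.3075, σ = 0.5545 and μ = ln m − σ²/2.

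- *Longest third:* mean true duration = 3·m·Φ(σ − 0.4307) = 3·m·0.5493, which is 32.96 h (BAC) and 28.01 h (PF). L is this minus c. The longest third starts at 21.8 h and 18.5 h, so every c used here does cut the course.
- *Random:* L = m − E[min(T, c)], where E[min(T, c)] = m·Φ(d − σ) + c·(1 − Φ(d)) and d = (ln c − μ)/σ.

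With 5% failures on PF, the recorded difference is zero when f_BAC = (3.0 + 0.05·L_PF)/L_BAC.

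| Failures from | Stop c (h) | L_BAC | L_PF | Recorded difference (h), 5% vs 5% | 10% vs 5% | 20% vs 5% | BAC failures giving zero |
|---|---|---|---|---|---|---|---|
| Longest third | 6 | 26.96 | 22.01 | 2.75 | 1.41 | −1.29 | 15% |
| Longest third | 12 | 20.96 | 16.01 | 2.75 | 1.71 | −0.39 | 18% |
| Longest third | 18 | 14.96 | 10.01 | 2.75 | 2.01 | 0.51 | 23% |
| Random | 6 | 14.03 | 11.06 | 2.85 | 2.15 | 0.75 | 25% |
| Random | 12 | 8.81 | 6.25 | 2.87 | 2.43 | 1.55 | 38% |
| Random | 18 | 5.22 | 3.34 | 2.91 | 2.64 | 2.12 | 61% |

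Worked example, longest third, c = 6, 10% vs 5%: 3.0 − 0.10 × 26.96 + 0.05 × 22.01 = 3.0 − 2.70 + 1.10 = 1.40 h (1.41 before rounding the inputs). A simulation of the same model agrees with the table to within a few hundredths of an hour.

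**Effect on power.** A second set of assumptions takes mean time to a recovery stop as 15 h (BAC) and 12 h (PF), SD 8 h, failure stops at about 6 h (SD 2 h), two-sided alpha 0.05, and 112 per arm, which gives 80% power for 3 h when nobody fails. PF failures are 5%, so the PF mean is 0.95 × 12 + 0.05 × 6 = 11.7 h.

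| BAC failures | BAC mean (h) | Recorded difference (h) | Power |
|---|---|---|---|
| 10% | 0.90 × 15 + 0.10 × 6 = 14.1 | 2.4 | 61% |
| 20% | 0.80 × 15 + 0.20 × 6 = 13.2 | 1.5 | 29% |
| 30% | 0.70 × 15 + 0.30 × 6 = 12.3 | 0.6 | 8% |

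Here the sign changes only when BAC failures pass (15 − 11.7)/(15 − 6) = 37%. With failure stops at 3 h the threshold is (15 − 11.55)/12 = 29%, and at 9 h it is (15 − 11.85)/6 = 53%.

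**The case against.** The plan does collect escalation, transfer, non-adherence and re-initiation, and it draws on the electronic record. Many failure stops could therefore be identified child by child, and an excess on BAC could appear in escalation, transfer or length of stay. This is right, and it limits the point to the primary comparison. It does not remove it: with no rule set in advance, how these children enter the primary outcome would be decided after the data are seen, and a signal in a secondary outcome does not correct a masked primary one.

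The mechanism also needs the event to end the recorded course. A reader might infer that transfer stops the clock, or that escalation replaces albuterol. The documents say neither. The outcome is length of administration, not time on the 5th floor. If timing continues in the receiving unit, a transferred child scores long, which is the sensible direction; if escalation is added to continuous albuterol, the course need not be cut. This objection stands as far as it goes, but two permissible readings that move the primary outcome in opposite directions are themselves the reason a definition is needed.

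A reader might also infer that the form has no field for the reason. Only the protocol's description can be judged, and that description does not claim to be complete.

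**Conclusion.** The point holds as a gap in the definition of the primary outcome and should be closed before enrolment. Taken literally, the plan lets a stop for failure or non-adherence enter the t-test as a short, favourable-looking duration.

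Masking is the supported conclusion. Under the assumptions shown, every scenario with more failures on BAC understates the 3.0 h difference: to about 1.4 to 2.6 h at 10% vs 5%, and to about −1.3 to 2.1 h at 20% vs 5%. In the second set of assumptions, power falls from 80% to 61% and 29% at those rates.

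The stronger reading, that the plan would reverse the sign and make BAC look better, is not supported. At 20% vs 5% it occurs only when failures come from the longest third of courses and are recorded at 6 or 12 h; the second set of assumptions needs 29% to 53% failures on BAC against 5%. Nor can it be said that the trial as a whole would miss the harm. All sizes rest on assumed durations and failure rates.

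**What to change.** 1. Record the reason for each stop on the form, if it is not there already: improvement, transfer, replaced by other therapy, non-adherence, other.
2. Define the primary outcome as time from first start to final stop for improvement. Restarted courses count within that span, and for transferred children the times in the receiving unit come from the electronic record.
3. Treat a child whose continuous albuterol ends for failure as not recovered, either ranked worse than every recovered child or as a competing event. Do not censor such a child at the stop, since that assumes later recovery like the others. State the rule for a non-adherence stop with no later stop for improvement, and check it in a sensitivity analysis.
4. For this outcome, replace the t-test with a rank test such as Wilcoxon (worst rank) or a time-to-event comparison (competing event). Report the raw mean duration as supportive, and base the power analysis, which is still to be done, on the chosen test.
5. Record the albuterol formulation given after transfer. The plan describes supply for the emergency department, 5 West and 5 East only.

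The cost is one form item, a look-up in a source already in use, and a short endpoint and analysis definition. These are changes to measurement and analysis, not to care. The price is that the primary result is no longer a simple difference in mean hours.

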A prospective, patient-blinded, randomized study will be conducted comparing patients admitted to Norton Children's Hospital for an asthma exacerbation. There will be no active recruitment of patients; however, eligible patients will be those who present to our emergency department in status asthmaticus. Patients will be randomly assigned to a patient room on 5 West versus 5 East upon admission based on bed availability. The Pyxis on 5 West will contain the standard multi-dose albuterol vial which contains BAC (current standard of care), while pharmacy will be preparing and dispensing PF-albuterol to patients on 5 East who are enrolled in the study. The treatment of patients will not vary between groups, nor deviate from the standard of care currently implemented at the institution. If a patient consents to study enrollment, he/she will receive PF-albuterol while awaiting bed assignment in the emergency department. This is essential to avoid confounding the results of the study, as BAC has a

prolonged half-life and may have clinical consequences even after a patient is randomized to receive PF-albuterol.

Informed consent will be required for all patients, and assent will additionally be required for patients between 7 and 17 years of age. The study will be explained by a study investigator or respiratory therapist (under the supervision of the respiratory therapy director) and informed consent/assent paperwork will be provided to the patient/caregiver while in the emergency department. Approximately 10-20 minutes will be allotted for the consent/assent process. The difference between groups is the formulation of albuterol being used, and both formulations have FDA approval for use in status asthmaticus.

INCLUSION AND EXCLUSION CRITERIA

Patients will be included in the study if they are admitted to the 5th floor at Norton Children's Hospital for the treatment of an acute asthma exacerbation, initiated on continuous albuterol inhalation therapy, and are between 3 and 17 years of age.

Patients will be excluded from the study if they are transferred to the 5th floor from any other unit except the emergency department, admitted for any indication other than acute asthma exacerbation, or exposed to BAC prior to admission.

DATA COLLECTION

Demographic information collected will include age, gender, weight, and ethnicity.

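### The primary comparison is an unadjusted t-test and makes no use of the admission asthma score as a baseline covariate, although the score is to be collected

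*Combined protocol and SAP*

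**What the plan says.** Under the statistical analysis heading, the protocol states that "comparison data will be analyzed using a two-tailed student t-test". No regression model, stratified analysis or covariate is named anywhere, and demographics are only to be described. The power analysis is still to be done.

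The Objective section fixes the endpoint that the test serves: "The primary objective of this study is to compare the length of continuous albuterol administration between patients receiving BAC-containing albuterol" and those receiving the preservative-free product.

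The Data Collection section lists the severity measure: "Additional parameters obtained will include admission asthma score", among other items. Asthma scores otherwise appear only in the Objective section: "Secondary objectives include comparison of therapy escalation, asthma scores, forced expiratory volume in one second", and further items.

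Two statements in the Methods section bear on this point. On allocation: "Patients will be randomly assigned to a patient room on 5 West versus 5 East upon admission based on bed availability". On treatment before allocation, a patient who consents is told that "he/she will receive PF-albuterol while awaiting bed assignment in the emergency department".

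**The concern.** A two-sample t-test ignores what is known about each child at entry. If the admission score predicts time on continuous albuterol, part of the outcome variance could be explained and removed, and the plan forgoes that gain.

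In a properly randomized trial the loss would be precision alone. Here the formulation follows the room, the room follows bed availability, and nothing balances severity between 5 West and 5 East. If the units receive children of different severity, the unadjusted difference in mean hours carries that difference with it. Of the items listed, the admission score is the only one that looks like a baseline severity measure.

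Timing matters too. All consented patients receive the preservative-free product until a bed is assigned, so the formulations differ only after that. A score charted before bed assignment is a true baseline. A later one may already reflect the formulation and should not be a covariate. The supplied text does not say when the score is taken.

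**Working it through.** **Inputs from the documents.** Endpoint: a duration. Test: two-sided Student t. Admission score: to be collected. Allocation: by bed availability. The documents state no sample size, SD, effect size, power or correlation, so there is no figure of the plan's own to reproduce.

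**Assumed inputs.** Two-sided 5% level; 80% power for the unadjusted test; equal arms of 15, 30 or 50; normal outcome; r (correlation of score with duration) from 0 to 0.5; d (systematic difference in mean score between the two units, in SD) of 0.2 to 0.3.

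**1. Precision, large samples.** Adjusting for one baseline covariate multiplies the residual SD by √(1 − r²), so

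power = Φ[(1.960 + 0.842)/√(1 − r²) − 1.960].

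- r = 0.2: 2.802/0.980 − 1.960 = 0.90, power 81.6%
- r = 0.3: 2.802/0.954 − 1.960 = 0.98, power 83.6%
- r = 0.4: 2.802/0.917 − 1.960 = 1.10, power 86.4%
- r = 0.5: 2.802/0.866 − 1.960 = 1.28, power 89.9%

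Equivalently, the required sample size is multiplied by 1 − r². For an assumed effect of 0.5 SD, 63 per arm falls to 58 at r = 0.3 and 48 at r = 0.5.

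**2. Precision, small samples.** The formula ignores the degree of freedom spent and chance imbalance in the covariate. The simulation used 40,000 trials per setting (Monte Carlo error about 0.2 points), with the effect set so that the unadjusted test has 80% power. Power of the model with the score alone:

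| Per arm | r = 0 | 0.1 | 0.2 | 0.3 | 0.4 | 0.5 |
|---|---|---|---|---|---|---|
| 15 | 78.2% | 78.9% | 80.2% | 82.0% | 85.1% | 88.4% |
| 30 | 79.4% | 79.5% | 80.9% | 82.9% | 85.5% | 89.4% |
| 50 | 79.4% | 80.0% | 81.0% | 83.4% | 85.9% | 89.6% |

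Break-even is near r = 0.2 at 15 per arm and near r = 0.1 at 50 per arm. Adding an uninformative age term at 15 per arm gives 76.5% at r = 0 and 80.4% at r = 0.3, so break-even rises to just under 0.3. Type I error at 15 per arm and r = 0.3 is 4.8% unadjusted and 4.9% with the score.

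**3. Bias.** A score difference of d SD between the units shifts the unadjusted difference by r × d SD of duration:

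- r = 0.2, d = 0.2: 0.2 × 0.2 = 0.04 SD
- r = 0.5, d = 0.3: 0.5 × 0.3 = 0.15 SD

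At 30 per arm the noncentrality under no treatment effect is the shift × √(30/2). That is 0.04 × 3.873 = 0.155 and 0.15 × 3.873 = 0.581. From the noncentral t distribution, the nominal 5% test then rejects 5.3% and 8.8% of the time.

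**The case against.** The strongest reply is that nothing here is wrong. The t-test is valid under fair allocation, and adjustment is an improvement rather than a correction. The bias argument borrows its force from the allocation method, which adjustment does not cure, and no passage says that severity differs between the units. Every enrolled child presents in status asthmaticus and is started on continuous albuterol, which may narrow the range of scores and lower r. At 15 per arm with r of 0.1 or less, adjustment loses power. All of this stands. It limits the claim to a recommendation and rules out any promise about the size of the gain.

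It can also be said that the score is not idle, because asthma scores are a secondary comparison. That is fair: it is unused only in the primary comparison. On timing, the plan notes that "The data collection sheet to be used is attached", and the sheet is not in the supplied text; it may say when the score is taken.

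Finally, if continuous albuterol starts in the emergency department, a score charted before bed assignment may fall after the outcome clock has started. It is still a legitimate covariate, because it precedes any difference in formulation, but it may predict total duration less well.

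None of this is a reason to leave the score out. The power at risk is small, and allocation by bed availability is a reason to want a severity adjustment named in advance.

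**Conclusion.** The concern holds as a recommended improvement, not as an error that invalidates the analysis. With the score alone, the assumed range runs from a loss of about 0.5 to 2 points of power if the score is uninformative to a gain of about 8 to 10 points at r = 0.5. Under the assumed imbalances, bias in the unadjusted difference is 0.04 to 0.15 SD of duration. These figures rest on assumed values of r, d, arm size and starting power and on a normal outcome; none can be checked against the documents. Adjustment addresses measured severity only. It leaves unmeasured severity, differences between the units and the allocation method as they are.

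**What to change.** Replace the single t-test clause, for the primary endpoint, with wording such as:

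> The primary analysis is a linear model for hours of continuous albuterol, with formulation and admission asthma score as terms. The effect is the adjusted difference in mean hours with its 95% confidence interval, tested two-sided at 5%. The unadjusted t-test on hours is reported alongside.

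Then settle these points before enrolment:

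- **Scale.** Hours keeps the difference in means that the t-test implies. If log hours is preferred, for instance because of skew, use it for both analyses and state that the effect is a ratio of geometric means.
- **Score.** Define it as the last score charted before the bed is assigned, and state how a missing score is handled. Use it as a baseline only, not as evidence on the secondary asthma-score objective.
- **Age.** Include it only if named in advance.
- **Power.** Base the sample size on the unadjusted comparison, since r is unknown.
- **Allocation.** Deal with assignment by bed availability separately.

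The cost is a wording change on data already listed, plus a time stamp for the score, or one extra form field if no score is charted before bed assignment. The power at risk is about 0.5 to 2 points if the score is uninformative, and about 3.5 points at 15 per arm if age is added and neither is informative.
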